ECG		•	•	• (only Day 3)	•		•	•		
IMP										
IMP administration										
Number of tablets	-	2	1 tablet each morning + evening							
Accountability								•		
SoC treatment										

^a Needs to be frozen at at least -20° C (-4° F) and sent to the central safety laboratory within 6 weeks.

^b Clinical status on a 9-category ordinal scale (as proposed by the WHO master protocol)

^c Including documentation of ICU admission and discharge times.

- d Existing local lab values obtained within 48 hours of randomization as well as locally obtained screening lab values can be used for assessment of eligibility.
- e At each time point only 1 nasopharyngeal swab and 1 sputum sample each will be taken. The viral load test will also be used as qualitative test (i.e. may be evaluated as absence or presence of virus in the quantitative SARS-CoV-2 assessments). Samples need to be frozen at at least -20° C (-4° F) and sent to the central virology laboratory within 7 days on dry ice.
- f Includes: Age≥65; cardiovascular disease (including hypertension), pre-existing pulmonary disease, diabetes, current treatment for malignancy or within the previous 3 years, immunosuppression (due to ongoing use of immunosuppressive drugs or existing disease leading to impaired immune status), body mass index.
- g Screening, randomization and first IMP administration can be performed the same day (Day 0). If screening is performed on Day 0, treatment will start with the evening dose.
- h Plasma sample for serology SARS-CoV-2 (IgG and IgA detection) should be frozen at at least -20° C (-4° F) and sent to the central safety laboratory within 6 weeks.
- i Confirmation of radiographic evidence of pulmonary infiltrates by chest X-ray or CT (only if done within the scope of routine clinical practice).
- j Confirmation of presence of any new viral or non-viral infection (this is not a protocol-required procedure, only documentation when done within the scope of routine clinical practice). Site of infection and source of culture will be recorded.
- k As performed during routine clinical practice in the center. Must include white blood cell count, platelet count, total bilirubin, alanine aminotransferase or gamma glutamyl transferase, serum creatinine, for women of childbearing potential: blood pregnancy test, and if the patient has known Gilbert syndrome: indirect [unconjugated] bilirubin.

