In Part 1, the primary endpoint will be displayed with frequency tables per stratification factor age (< or \geq 65 years) and antiviral therapy (no antivirals, Hydroxychloroquine and Chloroquine, all other antivirals) and overall. In addition, an odds ratio (OR) with an exact 2-sided 90% confidence interval will be conducted. The OR will be calculated adjusted for the stratification factors age (< or \geq 65 years) and antiviral therapy (no antivirals, Hydroxychloroquine and Chloroquine, all other antivirals).

Key secondary endpoints

Proportion of patients surviving without respiratory failure

Respiratory failure will be defined as the need of ICU, INV, high-flow oxygen or ECMO. Patients who are lost to follow-up or discontinue the trial on or before Day 13 (last treatment day) due to any reason other than death, and patients who discontinue with a last observed WHO clinical status no lower than that at Screening are considered respiratory failures. A sensitivity analysis will be performed for patients who discontinued before EoS, using the available information. Statistical analysis will follow the analysis of the primary endpoint.

Duration of ICU treatment until Day 28

The duration of ICU treatment until Day 28 will be analyzed in decimal days.

For patients who were transferred to ICU, the duration of ICU treatment will be calculated as [Time of discharge from ICU (date:hh:mm) - time of admission to ICU (date:hh:mm) + 1] / 1440. For patients who were discharged from ICU but readmitted the time from first admission until last discharge will be used. The time from investigator's decision to admit a patient to ICU until a patient is admitted will not be considered.

If the investigator decides that there is the medical need to admit a patient to the ICU but the patient is not admitted due to patient refusal, unavailability of ICU or due to rationing or triage decisions, the start time of ICU hospitalization will use the investigator's decision. The end of ICU duration will be imputed as Day 28 or, if ICU hospitalization occurs at a later study period, until end of actual ICU hospitalization.

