The following imputation of concurrent events in the preferred analysis of ICU duration, creating the most conservative assessment approach will be performed: a) for all death cases that have no recorded or known ICU hospitalization in this trial, start date will be imputed as date/time of death, end date will be imputed as Day 28 b) if ICU treatment is known and started before the date of death, start date will be the actual ICU submission, end date will be imputed as Day 28.

For patients who are lost to follow-up or discontinue the trial on or before Day 13 (last treatment day) due to any reason other than death and patients who discontinue with a last observed WHO clinical status no lower than that at Screening, the following approach will be performed: a) for cases that have no recorded or known ICU hospitalization in this trial, start date will be imputed as date/time of discontinuation, end date will be imputed as Day 28 b) if ICU treatment is known and started before the date of study discontinuation, start date will be imputed as actual ICU submission, end date will be imputed as Day 28.

As sensitivity analyses, ICU duration imputation on available data will be done as follows:

- for patients who died, the study period of 28 days will be recorded as ICU treatment duration,
- for patients who discontinued the study prematurely or for patients who died before EoS, the available information on ICU treatment duration until day of discontinuation will be used.

In Part 1, the ICU duration will be displayed with basic statistics per stratification factor age (< or \geq 65 years) and antiviral therapy (no antivirals, Hydroxychloroquine and Chloroquine, all other antivirals) and overall. In addition, an exact 2-sided 90% confidence interval for the median of differences between treatment groups (location shift) will be conducted adjusted for the stratification factors age and antiviral therapy.

28-day all-cause mortality

28-day all-cause mortality will be derived as percentage of patients who died due to any cause from time of 1st IMP administration until EoS. In Part 1, 28-day all-cause mortality will be displayed with frequency tables per stratification factor age (< or \geq 65 years) and antiviral therapy (no antivirals, Hydroxychloroquine and Chloroquine, all other antivirals) and overall. In addition, an OR with exact 2-sided 90% confidence interval will be conducted. The OR will be calculated adjusted for the stratification factors.

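### For readmitted patients, mainly survivors who stay in the trial, time out of ICU between stays is scored as ICU treatment

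*Combined protocol and SAP*

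**What the plan says.** Section 16.3.2 sets the scale: "The duration of ICU treatment until Day 28 will be analyzed in decimal days". For a patient transferred to ICU the value is "Time of discharge from ICU (date:hh:mm) - time of admission to ICU (date:hh:mm) + 1] / 1440", which is a calculation to the minute. Readmission has its own rule: "For patients who were discharged from ICU but readmitted the time from first admission until last discharge will be used". The sentence after that deals with waiting time before an actual admission: "The time from investigator's decision to admit a patient to ICU until a patient is admitted will not be considered".

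Three groups have separate rules in the same section:

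- **Deaths.** If there was a known ICU stay, "start date will be the actual ICU submission, end date will be imputed as Day 28". If there was none, the interval runs from death to Day 28.
- **Certain discontinuations.** These are treated in the same way, with discontinuation in place of death.
- **Unmet ICU need.** The interval starts at the investigator's decision and runs to Day 28, or to the end of a later actual ICU stay.

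There are two sensitivity analyses. In one, "for patients who died, the study period of 28 days will be recorded as ICU treatment duration". In the other, for premature discontinuations and deaths, "the available information on ICU treatment duration until day of discontinuation will be used".

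On data capture, footnote c to the schedule of assessments (Table 3 in Section 12.1, repeated in Table 1) reads "Including documentation of ICU admission and discharge times".

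**The concern.** The endpoint is named as a duration of ICU treatment, but for a patient with two stays the rule measures the interval that contains both. Someone with two short stays a week apart gets the same value as someone who was in ICU throughout. The plan also handles time out of ICU in two ways: it is left out before an actual admission and counted between admissions.

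The endpoint is used in several places. It is a key secondary endpoint with a 90% location-shift interval in Part 1 (Section 16.3.2). It is also one of three ways to show a moderate key secondary effect in the activity decision at the main analysis, where the median should be about 1.5 days or more shorter on IMU-838 (Section 16.4.2). In Section 16.3.2 it is the example given for the van Elteren test in Part 2. If the definition does not measure time in ICU, none of these results can be read as a statement about ICU time for readmitted patients.

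**Working it through.** No sample size, power or alpha in the plan depends on this rule, so there is no planned figure to reproduce. The check applies the Section 16.3.2 formula to a patient with two stays.

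**Formulas.** Let A1, D1 and A2, D2 be the admission and discharge times of the two stays, in minutes.

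- Plan's rule: [(D2 − A1) + 1] / 1440.
- Sum of stays: [(D1 − A1) + 1] / 1440 + [(D2 − A2) + 1] / 1440.
- Difference: [(A2 − D1) − 1] / 1440, which is the gap between stays less one minute.

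**Example (hypothetical).** ICU from Day 3 to Day 5 and from Day 14 to Day 16, all at the same clock time.

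- Plan's rule: 16 − 3 = 13 days (13.0007 with the added minute).
- Sum of stays: (5 − 3) + (16 − 14) = 4 days (4.0014 with one minute per stay).
- Excess: 13 − 4 = 9 days, equal to the gap 14 − 5 = 9.

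A patient in ICU continuously from Day 3 to Day 16 also scores 13.

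**Excess by gap length, to two decimals.**

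| Gap (days) | 1 | 2 | 5 | 10 | 15 |
|---|---|---|---|---|---|
| Excess (days) | 1.00 | 2.00 | 5.00 | 10.00 | 15.00 |

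**Who is affected.** Patients who die or meet the discontinuation rule after an ICU stay already have their end date set to Day 28, so the readmission rule does not fix their value in the preferred analysis. Unmet ICU need also has its own rule. What remains is readmitted patients outside those rules, mainly survivors who stay in the trial. The time between stays can be ward time anywhere. Home time is also possible because Section 12.3 provides for discharge before Day 14, except at Bulgarian centers, where patients stay in hospital from Day 0 to Day 14.

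**Effect on a mean.** The documents give no readmission rate or gap length. Assume that a share r of ICU patients is readmitted with mean gap g. Mean duration among an arm's ICU patients then rises by r × g:

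- r = 5%, g = 2 days: 0.05 × 2 = 0.1 day.
- r = 10%, g = 5 days: 0.10 × 5 = 0.5 day.
- r = 20%, g = 10 days: 0.20 × 10 = 2.0 days.

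These are within-arm shifts under assumed inputs. The between-arm effect on that mean is the difference between the two arms' r × g. It is zero if these are equal, and it cannot be determined from the documents.

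**Effect on a median.** The plan does not state the value for patients never in ICU. If it is 0, and fewer than half of an arm has a non-zero value (actual or imputed), the arm median is 0 and gaps do not move it.

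**Sensitivity analyses.** Both change how deaths or discontinuations are scored. Neither replaces the span with a sum of stays.

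**The case against.** The rule is explicit and pre-specified, and nothing in the plan defines the endpoint as summed ICU time. This is therefore a choice of definition and not a contradiction between sections. That stands. A span could be defended as the length of a critical episode, but the plan does not say so. Its appeal to a conservative approach introduces the imputation of concurrent events, whereas a readmitted patient with recorded times needs no imputation.

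The influence on decisions is limited, and that stands too. Part 1 has no formal tests. The ICU criterion is approximate, is one of three alternatives, and counts only alongside at least a 10% relative effect on the primary endpoint. An overall consistent pattern is also required (Section 16.4.2), and endpoints may change for Part 2.

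A reader might infer more in three ways, none of which the documents support:

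- **That the treatment comparison is biased.** The rule is identical in both arms of a double-blind trial. It distorts the contrast only if readmissions or gaps differ by arm, and no data on this are given.
- **That a 9-day excess can be set against the 1.5-day threshold.** The first is one patient's value and the second is a difference between arm medians. With about 100 patients per arm, one patient's value moves a median by about one rank at most. Neither the location-shift interval nor the van Elteren test is driven by the size of a single outlying value.
- **That sicker patients in general are misscored.** Those who die or meet the discontinuation rule are governed by the Day-28 imputations.

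One caution on the data also stands. Footnote c does not say that every stay is captured, and after Day 14 the next scheduled ICU-status entry is Day 28. Full capture of stays in that window is plausible but inferred.

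**Conclusion.** The point holds as a modest one. For readmitted patients outside the Day-28 imputation rules, the endpoint overstates time in ICU by the length of the gap between stays, and no planned analysis shows by how much. The excess for an individual follows exactly from the written formula. The group-level effect does not: the 0.1 to 2.0 day range for a within-arm mean among ICU patients rests on assumed readmission shares of 5% to 20% and mean gaps of 2 to 10 days. The effect on arm medians may be small, while means and rank-based results could change. Neither the direction nor the size of any between-arm effect can be determined. The change is worth making because it lets a key secondary endpoint measure what it names at little cost, not because the plan's conclusions are shown to be at risk.

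**What to change.** In Section 16.3.2, for readmitted patients replace the first-to-last span with the sum of (discharge − admission) over the separate ICU stays up to Day 28. State whether the added minute applies once or per stay; the difference is trivial. State also that the rules for death, discontinuation and unmet ICU need are unchanged and take precedence where they apply. Keep the first-to-last span as a sensitivity analysis if it is wanted.

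The cost is a small revision of protocol and SAP wording for a key secondary endpoint, plus one derivation. Section 16.3.1 has the detailed SAP finalized before the respective data are analyzed, so the change can be aligned there. It relies on the ICU admission and discharge times that footnote c already requires. Before it is adopted, confirm that the eCRF records each stay separately, including any between Days 14 and 28.

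### ICU duration runs to Day 28 for a patient never given an ICU bed, even after live discharge, and two adjacent rules disagree on whether a wait for a bed counts

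*Combined protocol and SAP*

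**What the plan says.** All of this is in the combined protocol and SAP, Section 16.3.2, under the key secondary endpoint of ICU treatment duration until Day 28.

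- **Basic derivation**, for patients transferred to ICU: "Time of discharge from ICU (date:hh:mm) - time of admission to ICU (date:hh:mm) + 1] / 1440". That paragraph closes with: "The time from investigator's decision to admit a patient to ICU until a patient is admitted will not be considered".
- **Unmet need**, next paragraph. It applies when ICU is judged medically necessary but "the patient is not admitted due to patient refusal, unavailability of ICU or due to rationing or triage decisions". In that case "the start time of ICU hospitalization will use the investigator's decision".
- **End of the unmet-need stay**: "The end of ICU duration will be imputed as Day 28 or, if ICU hospitalization occurs at a later study period". In the latter case, a patient admitted after all is counted to the true end of the stay.
- **Sensitivity analyses**: these cover deaths and premature discontinuation only, for example "for patients who discontinued the study prematurely or for patients who died before EoS, the available information on ICU treatment duration", counted up to the day the patient left the study. None addresses unmet ICU need.

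In Part 1 the endpoint is described with a stratified 90% confidence interval for the location shift, with no formal test (Sections 16.3.1 and 16.3.2). In the second limb of the activity criteria (Section 16.4.2), a median ICU duration about 1.5 days shorter on IMU-838 can serve as the supporting key secondary effect next to a mild primary effect. In Part 2, duration endpoints would be analyzed with the van Elteren test (Section 16.3.2).

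**The concern.** There are two separate faults.

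First, the Day 28 end for a never-admitted patient ignores what happened next. Imputing to Day 28 can be defended as conservative for a death or a dropout, which is how Section 16.3.2 justifies it for those cases. A patient who was refused a bed, improved on the ward and went home is neither. Follow-up is complete and the outcome is good, yet ICU days keep accruing while the patient is at home.

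Second, a patient who waits because of refusal, unavailability or triage and is then admitted falls under both paragraphs. One excludes the wait and the other starts the clock at the decision. Two programmers could derive different values from the same record.

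At stake is a key secondary endpoint that can help decide whether Part 2 starts and that would be tested confirmatorily in Part 2 if retained. The protocol itself foresees resource exhaustion and triage (Section 16.3.2, need for INV), so such patients are not hypothetical. No planned analysis would show how much of the result they contribute.

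**Working it through.** The plan gives no unmet-need rate and no ICU-stay distribution, so there is no plan figure to reproduce. The check applies the written rules to single patients, then uses simulation under stated assumptions.

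**Single patients** (duration = end minus start; the added minute is 1/1440 = 0.0007 day and is ignored)

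| Course | Rule applied | ICU days |
|---|---|---|
| Need Day 4, admitted at once, out Day 9 | basic | 9 − 4 = 5 |
| Need Day 4, never admitted, home Day 12 | unmet need | 28 − 4 = 24 |
| Need Day 4, admitted Day 6, out Day 9 | wait excluded | 9 − 6 = 3 |
| Same patient | clock starts at decision | 9 − 4 = 5 |

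The never-admitted patient is charged 28 − 12 = 16 days after going home. For the delayed patient the two readings differ by 2 days, more than the 1.5-day activity threshold, though that threshold applies to medians and not to one patient.

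**Simulation 1: loss of sensitivity.** Assumptions: 100 per arm; ICU need 32% v 40% (the INV rates in Section 16.1, used as a stand-in); median need 5.5 v 8 days, lognormal with sigma 0.6, cut at Day 28; onset Days 1–10; patients without ICU need scored 0; the same unmet share in both arms; 3,000 trials per row; no stratification.

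| Unmet share | Placebo mean (days) | Placebo SD | 90% CI of mean difference favors IMU-838 | Wilcoxon, one-sided 5%, favors IMU-838 | All-patient median difference reaches 1.5 days |
|---|---|---|---|---|---|
| 0% | 3.7 | 5.6 | 78% | about 56% | about 2% |
| 10% | 4.2 | 6.5 | 63% | about 51% | about 2% |
| 20% | 4.7 | 7.3 | 53% | about 46% | about 2% |
| 30% | 5.3 | 8.0 | 47% | about 42% | about 2% |

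The mean-based interval loses 78 − 47 = 31 points, but the plan does not use it. A rank test, closer to the planned method, loses about 56 − 42 = 14 points. The location-shift estimate is exactly 0 in about 99.9% or more of trials at every unmet share, because most patients have no ICU time.

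**Simulation 2: no true effect.** Assumptions: onset Days 1–14, median need 8 days (sigma 0.7), 1,500 trials.

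- ICU need 40% in both arms: the all-patient median difference averages within 0.1 day of 0, with or without the rule.
- ICU need 60% in both arms: still no average bias. The SD of the all-patient median difference rises from 1.6 days to 2.0 (25% unmet) and 3.1 (50% unmet).
- Medians among ICU-need patients only, 40% need: the chance of an apparent 1.5-day benefit is about 16% on actual stays and 20%, 31% and 24% at 10%, 25% and 50% unmet.
- Same setting, with 10% unmet on IMU-838 and 20% on placebo: that median shifts by about 1.2 days in favor of IMU-838, and the chance becomes 44% against 17% on actual stays.

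Section 16.4.2 does not say whether its median covers all patients or only those with ICU need. The size of the effect depends on that.

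**The case against.** **The endpoint is not shown to be driven by bed supply.** A reader might infer that bed availability determines this endpoint, or that the endpoint measures hospital capacity rather than illness. The documents do not support that. They give no unmet-need rate, patient refusal is also a trigger, and central, double-blind 1:1 allocation (Section 8.1) makes access to beds equal between arms in expectation. What remains is noise and chance imbalance; neither center nor country is a stratification factor. This objection stands.

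**The planned methods damp outliers.** A location-shift interval, a rank test and a median threshold react far less to a value of 24 than a mean does. This stands, and it is why the mean-based loss above should not be quoted as the effect on the plan.

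**The two sentences may be a general rule and an exception.** The first closes the paragraph on transferred patients; the second concerns patients not admitted for listed reasons. That is a fair reading for patients who are never admitted. It fails for those admitted later, because the second paragraph expressly includes them. So the conflict is real but limited to delayed admissions. The Day 28 end, conversely, does not apply to them: they stop at actual ICU discharge.

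**The stakes are limited.** Part 1 is descriptive, Part 2 endpoints may change (Section 16.3.2), and a detailed SAP is to be finalized before each analysis (Section 16.3.1). This lowers the urgency, but the rule is stated explicitly and would give wrong values if programmed as it stands.

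**Conclusion.** Wrong as written. A never-admitted patient with unmet ICU need is charged to Day 28 whatever the later course, and delayed admissions have two incompatible start rules. For single patients the error can be large (24 days with 16 of them at home; 3 v 5 days). For the trial the expected effect is added noise, not bias between arms.

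Under the assumptions shown, a rank-based comparison loses roughly 5 to 14 percentage points of sensitivity at 10% to 30% unmet need, and the all-patient median hardly moves while fewer than half of patients need ICU. The effect is larger if the activity threshold is applied to ICU-need patients only, or if unmet need happens to differ between arms. All these sizes are conditional on assumed rates, since the documents supply none. The two defects in the text do not depend on them.

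**What to change.** Make three changes to Section 16.3.2, carried into the SAP before MA1 unblinding:

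1. **End date for never-admitted patients.** End the imputed stay at live hospital discharge if it occurs before Day 28, otherwise at Day 28. Leave deaths as the section already treats them. The example patient then scores 12 − 4 = 8 days. Do not use a WHO score of 4 or lower as the end of need. The score is scheduled daily only to Day 14 and then on Day 28 (Table 3). Patients enter at category 3 or 4 (Section 9.2), so someone denied ICU and kept on mask oxygen might never exceed 4 and would score about 0.
2. **One start rule for delayed admissions.** Use the investigator's decision when the delay is due to refusal, unavailability, rationing or triage. Limit the sentence excluding the wait to routine transfer time.
3. **Sensitivity analyses.** Add one on actual ICU time only and one on the current Day 28 rule.

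The cost is a few lines of text and a short derivation. ICU admission and discharge times are recorded (Table 3, footnote c), and hospital discharge is needed anyway for duration of hospitalization. ICU days become slightly less conservative for patients not given a bed. In Bulgaria, where patients stay in hospital to Day 14, the new end date cannot fall before then.

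### The preferred ICU-duration rule for deaths is labelled the most conservative, yet it can score a late death as only a few ICU days, better than some living patients and far below the plan's own 28-day sensitivity value

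*Combined protocol and SAP*

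**What the plan says.** Protocol section 16.3.2 measures ICU duration to Day 28 in decimal days, and it is a key secondary endpoint. The rules that matter here are these.

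- **ICU patients in general.** "For patients who were transferred to ICU, the duration of ICU treatment will be calculated as" discharge minus admission. With readmissions, the span from first admission to last discharge is used.
- **ICU needed but not given** (refusal, no bed, rationing or triage). Here "the start time of ICU hospitalization will use the investigator's decision", and the end is Day 28 unless an actual ICU stay follows.
- **Deaths, preferred analysis, rule (a).** "for all death cases that have no recorded or known ICU hospitalization in this trial, start date will be imputed as date/time of death"; the end is Day 28.
- **Deaths, preferred analysis, rule (b).** If ICU treatment is known and began before death, "start date will be the actual ICU submission, end date will be imputed as Day 28".
- **Label.** The section introduces these imputations as "creating the most conservative assessment approach will be performed".
- **Non-death dropouts.** For anyone who leaves on or before Day 13, the same scheme applies with the discontinuation time in place of the time of death.
- **Sensitivity analyses.** One bullet reads "for patients who died, the study period of 28 days will be recorded as ICU treatment duration". A second uses the observed ICU time up to discontinuation or death.

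In Part 1 the endpoint is summarised by a stratified location shift with a 90% interval and no test. In Part 2, as currently written, it is tested with the van Elteren test. Section 16.4.2 also uses it as one of three alternative key-secondary legs of the second activity criterion (median about 1.5 days shorter on IMU-838).

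**The concern.** Small values are good on this endpoint, so a conservative rule for deaths should place them at or near the bad end. Rule (a) does so only for early deaths. The value falls by one day for each day the death comes later, so a ward death near Day 28 looks like a very short ICU stay. Rule (b) has a related weakness when ICU admission itself is late.

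The stake is the ordering. If some deaths rank better than some living patients, a difference in ICU duration no longer has a clear direction. A shorter duration in one arm could partly reflect late deaths with little or no ICU time. The label also matters, because a reader of the report would take the preferred analysis as the worst case when a stricter rule is listed as a sensitivity analysis.

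**Working it through.** The plan states no figure to reproduce, so the scoring rules are applied directly. All inputs are from section 16.3.2 unless marked as assumed. Day numbers are treated as whole days.

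**1. Deaths without ICU, rule (a).** Score = 28 − day of death.

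| Day of death | Preferred rule | 28-day sensitivity rule |
|---|---|---|
| 5 | 23 | 28 |
| 10 | 18 | 28 |
| 14 | 14 | 28 |
| 20 | 8 | 28 |
| 25 | 3 | 28 |
| 27 | 1 | 28 |

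The gap between the two rules equals the day of death: 28 − (28 − d) = d.

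**2. Deaths after ICU admission, rule (b).** Score = 28 − day of admission, whatever the day of death. Admission on Day 5 gives 23. Admission on Day 25 with death on Day 26 gives 3.

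Across both rules the 28-day value is never smaller than the preferred value, and it is larger for every death or ICU admission after Day 0. At patient level the label is therefore wrong.

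**3. Comparison with living patients, using the plan's rules only.**

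- A non-ICU patient who discontinues on or before Day 13 scores at least 28 − 13 = 15. A non-ICU death on Day 14 or later scores at most 28 − 14 = 14. Every such dropout ranks worse than every such death, even if the dropout is later confirmed alive.
- A survivor who needed ICU on Day 10 and was never admitted, for one of the listed reasons, scores 28 − 10 = 18. A non-ICU death on Day 25 scores 3.

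**4. Comparison with ICU survivors (stay S assumed).** A non-ICU death on Day d scores better than a survivor with stay S when 28 − d < S, that is, when d > 28 − S.

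| Assumed ICU stay S (days) | Non-ICU deaths score better after Day |
|---|---|
| 3 | 25 |
| 5 | 23 |
| 7 | 21 |
| 10 | 18 |
| 14 | 14 |

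**5. Can the direction of a rank comparison change?** Illustration with assumed data: 100 patients per arm, 75 in each arm scoring 0, no stratification. Arm A has 25 survivors with 10 ICU days. Arm B has 25 non-ICU deaths on Day 25. U counts the pairs in which the arm A patient has the longer duration, with ties as one half.

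- Preferred rule (deaths score 3): U = 25 × 100 + 0.5 × 75 × 75 = 2500 + 2812.5 = 5312.5 of 10,000. The arm with the deaths looks better (one-sided p = 0.157).
- 28-day rule: U = 25 × 75 + 2812.5 = 1875 + 2812.5 = 4687.5. The direction reverses by the same amount.

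The case is deliberately extreme. It shows that the choice of rule can set the direction, not how large the effect would be in this trial.

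**The case against.** Several points on the other side have weight.

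- **Early deaths are scored high** (Day 5 = 23), so the problem is confined to late deaths without ICU and deaths after late ICU admission. This stands.
- **Unmet ICU need has its own rule.** If the investigator recorded a need for ICU that was not met for a listed reason, the clock starts at that decision. This takes many such deaths out of rule (a), provided it overrides the death rule, which the section does not say. A late decision still gives a short duration.
- **Conservative for a patient is not always conservative for the contrast.** If the active arm has fewer deaths, 28 days per death can enlarge its apparent benefit. This stands, so the criticism of the label is made at patient level only.
- **Other endpoints would expose excess deaths.** Every death is a failure for the primary endpoint, and mortality and survival without respiratory failure are separate key secondaries. The ICU leg in section 16.4.2 counts only alongside a relative difference of at least 10% on the primary endpoint, and every scenario requires a consistent overall pattern.
- **The summary may not move.** If patients without ICU score 0 (assumed; the text does not say) and fewer than half of each arm have non-zero values, the difference in medians and the unstratified location-shift estimate are both 0 under either death rule. The illustration above, with 25 non-zero per 100, is such a case: only the rank statistic changes.
- **The stricter rule is already prespecified**, so the discrepancy would show in the report. That reduces the harm but leaves the weaker rule as the preferred one.

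A reader might infer three stronger things that the documents do not support. First, that every later death scores lower: under rule (b) the score depends on admission, not on the day of death. Second, that prolonging survival is being counted as harm, or harm as benefit: a later death is not itself harm, and the anomaly is only the ranking against living patients. Third, that the two sensitivity bullets contradict each other: the plural wording fits two separate analyses, and they merely lack labels.

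**Conclusion.** The point holds in a limited form. The preferred rule is not the most conservative one at patient level, since a stricter rule stands in the same section. The shortfall equals the day of death under rule (a), or the day of ICU admission under rule (b), and so reaches 27 days for a Day 27 ward death. Some deaths rank better than some living patients. The comparison with early dropouts shows this without any outside assumption.

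The effect on the trial's conclusions cannot be quantified. The documents give no distribution of ICU stays or death days and no expected share of non-zero values. A statement that many ICU survivors would score worse than deaths rests on an assumed stay: for stays of 3 to 14 days, the crossover runs from Day 25 down to Day 14. It would also go too far to say that the activity decision would be changed, because the 1.5-day median leg may not move at all. The location-shift estimate is exposed when enough patients have non-zero values. The van Elteren ranking is exposed more generally, if the endpoint and test are kept for Part 2, which section 16.3.2 leaves open.

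This should be corrected, but it does not threaten the primary endpoint.

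**What to change.** In protocol section 16.3.2 and in the statistical analysis plan, before MA1 is unblinded:

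1. In the preferred analysis, assign 28 days (the worst value) to all deaths before end of study. Provided survivors' durations are cut at Day 28, no death can then rank better than a survivor. A Day 25 ward death moves from 3 to 28.
2. Move the current date-based rules (a) and (b) for deaths to a sensitivity analysis.
3. List the 28-day rule and the observed-time rule as separate, numbered analyses.
4. Drop the claim that the approach is the most conservative, or restrict it to patient-level values.

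The cost is small: the two rules already specified change places, with no new data, visits or sample size. Because the rule sits in the protocol, the protocol text must change as well as the analysis plan. The real downside is statistical: with 28 days per death the endpoint overlaps more with 28-day mortality, so the date-based and observed-time results should be reported beside it.
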